10.4 Appendix: Protocol Amendment History

The Protocol Amendment Rationale for the current amendment is located directly before the Table of Contents.

Protocol Update from Version 1.0 (01 August 2022) to Version 2.0 (13 October 2022):

The updates of protocol version 1.0 to protocol version 2.0 were administrative with the purpose of correction of errors, harmonization of text, and updating information.

Protocol Amendment 1: from Version 2.0 (13 October 2022) to Version 3.0 (26 June 2023):

The updates of protocol version 2.0 to protocol version 3.0 were administrative with the purpose of including clinical sites in the United States in addition to sites in Puerto Rico.

10.5 Appendix: Abbreviations

AE	adverse event
AESI	adverse event of special interest
AR	adverse reaction
ARI	acute respiratory illness
CDISC	Clinical Data Interchange Standards Consortium
CI	confidence interval
CIOMS	Council for International Organizations of Medical Sciences
CRB	case report book
CRF	case report form
DC	diary card
DNA	deoxyribonucleic acid
ELISA	Enzyme-linked Immuno-adsorbant Assay
FAS	full analysis set
GCP	Good Clinical Practice
GDPR	General Data Protection Regulation
GMT	geometric mean titer
GMTR	geometric mean titer ratio
GPV	Global Pharmacovigilance
HIV	human immunodeficiency virus
IB	Investigator's Brochure
ICF	informed consent form
ICH	International Council for Harmonisation
IDFU	investigational directions for use
IEC	Independent Ethics Committees
IMP	investigational medicinal product
IR	Investigator Registry
IRB	Institutional Review Boards
IRT	Interactive Response Technology
LAR	legally acceptable representative
LRI	lower respiratory infection

MAAE	medically attended adverse event
MAARI	medically attended acute respiratory illness
MedDRA	Medical Dictionary for Regulatory Activities
NC	negative control
NIH	National Institutes of Health
NIMP	non-investigational medicinal product
NS	nasal swab
PFU	plaque forming units
PIAF	Protocol Investigator Agreement Form
PPAS	per-protocol analysis set
PV	pharmacovigilance
qRT-PCR	quantitative reverse transcriptase polymerase chain reaction
QTL	quality tolerance limit
RMO	Responsible Medical Officer
RNA	ribonucleic acid
RSV	Respiratory Syncytial Virus
SAE	serious adverse event
SafAS	safety analysis set
SAP	statistical analysis plan
SIP	Shared Investigator Platform
SoA	schedule of activities
SUSAR	suspected unexpected serious adverse reactions
TBD	to be determined
URI	upper respiratory infection
VTM	Viral Transport Media
WT	wild type

## Version History

Not applicable as this is the first version of the SAP Core Body.

## 1 Overall Design

In the context of intranasal administration of a live attenuated Respiratory Syncytial Virus (RSV) vaccine and to demonstrate that a large-scale study with the RSVt vaccine can be conducted safely, both the transmission rate and the genetic stability of the vaccine virus will be determined. In addition, the vaccine virus shedding will be described in the RSVt vaccinees at regular timepoints and the clinical safety in their close contacts will be assessed.

Data generated in the VAD00014 study will provide insights into the transmission of the RSVt vaccine virus and genetic stability, along with the safety and immunogenic profile of the RSVt vaccine candidate, and may support the next steps of the development, including the planned large-scale Phase III efficacy study.

The design of the study is summarized in [Table 1.1](#) and in [Figure 1.1](#):

**Table 1.1: Design**

Type of design	Parallel, multi-center
Phase	II
Control method	Placebo-controlled
Study population	

Pediatric participants: Healthy infants / toddlers 6 to < 24 months of age in close contact with other infants / toddlers 6 to < 24 months of age who will participate in the study

Ad-hoc close contact participants: Ad-hoc close contact children and adults who experience acute respiratory illness (ARI) in the 28 days following the administration of the study intervention to the close contact pediatric participant

Level and method of blinding	Observer-blind: 

Blinding for study intervention group assignment: participants, parents or legally acceptable representative (LAR), outcome assessors, investigators, laboratory personnel, Sponsor study staff

No blinding for study staff who prepare and administer the study interventions

Study intervention assignment method	Pediatric participants will be screened for eligibility criteria at the time of inclusion and randomized to receive either RSVt vaccine or placebo in a 1:1 ratio. Randomization will be stratified by contact group (the household /group attended in daycare center) and by age group (< 12 months / ≥ 12 months)

Number of participants	100 pediatric participants 6 to < 24 months of age
Intervention groups	Eligible pediatric participants will be randomized in a 1:1 ratio to receive 2 intranasal administrations (56 days apart) of either the RSVt vaccine or placebo at D01 and D57
Total duration of study participation	Approximately 8 months for each pediatric participant. The duration of the ad-hoc close contacts will be limited to the Illness Visit.
Countries	United States and Puerto Rico
Use of an Independent Data Monitoring Committee, Dose Escalation Committee, or similar review group	NO

**Table 1.2: Schedule of activities for pediatric participants**

Phase II Study, 11 Planned Visits, 2 Vaccinations, 3 Blood Samples, 9 Planned Nasal Swabs, One 6-Month Safety Follow-up Phone Call, approximately 8 Months' Duration Per Pediatric Participant

Visit/Contact*	Collection of information in the CRF	V01	V02	V03	V04	V05	V06	V07	V08	V09	V10	V11	Safety followup phone call	Illness Visit‡‡
Study timelines days (D)		D01	D04	D08	D11	D15	D18	D22	D57	D64	D71	D85	D237	
Visit Interval			V01 + 3d	V01 + 7d	V01 + 10d	V01 + 14d	V01 + 17d	V01 + 21d	V01 + 56d	V08 + 7d	V08 + 14d	V08 + 28d	V08 + 6 months	
Time windows (days)		NA	[+1]	[+1]	[+1]	[+1]	[+1]	[+1]	[+7]	[+1]	[+1]	[+7]	[+14]	
Visit procedures:														
Informed consent	X	X												
Inclusion/exclusion criteria	X	X												
Collection of demographic data	X													
Collection of medical history	X Significant Medical History	X												
Physical examination	X	X							X					
Vital signs†	X	X							X					
Rapid COVID-19 test	X	X							X					

Visit/Contact*	Collection of information in the CRF	V01	V02	V03	V04	V05	V06	V07	V08	V09	V10	V11	Safety followup phone call	Illness Visit‡‡
Study timelines days (D)		D01	D04	D08	D11	D15	D18	D22	D57	D64	D71	D85	D237	
Visit Interval			V01 + 3d	V01 + 7d	V01 + 10d	V01 + 14d	V01 + 17d	V01 + 21d	V01 + 56d	V08 + 7d	V08 + 14d	V08 + 28d	V08 + 6 months	
Time windows (days)		NA	[+1]	[+1]	[+1]	[+1]	[+1]	[+1]	[+7]	[+1]	[+1]	[+7]	[+14]	
Collection of reportable concomitant medications/vaccinations	X								X					X
Randomization/allocation of participant number	X	X												
Dose number	X	X							X					
Blood sampling (BL) [5 mL]	X	BL0001 Pre-vac1							BL0002 Pre-vac2			BL0003		
Nasal swab (NS)‡	X	NS0001 Pre-vac1	NS0002	NS0003	NS0004	NS0005	NS0006	NS0007		NS0008	NS0009			UN0001 to UN000X
Vaccination (vac)	X	VAC1							VAC2					
Immediate surveillance (30 min)§	X	X							X					
DC provided**		DC1							DC2					
DC reviewed††			DC1	DC1	DC1	DC1	DC1	DC1	DC1	DC2	DC2	DC2		
DC collected									DC1			DC2		
MA provided												MA		
MA reviewed												MA		
Collection of solicited administration site and systemic reactions	X	From D01 to D22							From D57 to D78					

Visit/Contact*	Collection of information in the CRF	V01	V02	V03	V04	V05	V06	V07	V08	V09	V10	V11	Safety followup phone call	Illness Visit†‡
Study timelines days (D)		D01	D04	D08	D11	D15	D18	D22	D57	D64	D71	D85	D237	
Visit Interval			V01 + 3d	V01 + 7d	V01 + 10d	V01 + 14d	V01 + 17d	V01 + 21d	V01 + 56d	V08 + 7d	V08 + 14d	V08 + 28d	V08 + 6 months	
Time windows (days)		NA	[+1]	[+1]	[+1]	[+1]	[+1]	[+1]	[+7]	[+1]	[+1]	[+7]	[+14]	
Collection of unsolicited AEs	X	From D01 to D29							From D57 to D85					
Collection of AESIs and MAAEs	X	From D01 to D29							From D57 to D85					
Collection of SAEs	X	Throughout the study												
Phone Call													X	
Collection of End of Study Intervention Phase status	X												X	
Collection of 6-Month Follow-up-End of Study status	X												X	

Abbreviations: AE, adverse event; AESI, adverse event of special interest; COVID-19, coronavirus disease 2019; CRF, case report form; DC: diary card; LAR, legally acceptable representatives; MA, memory aid; MAAE, medically-attended adverse event; NA, not applicable; SAE, serious adverse event.

\* Additional unscheduled visits may be performed for safety reasons; information will be reported in the source documents.

† Vital signs will be collected in the eCRF.

‡ All pediatric participants will provide a nasal swab sample for detection of vaccine virus shedding / transmission at specified visits. The same nasal swab specimen may also be tested for respiratory pathogens (including COVID-19), if the pediatric participant is ill at the time of the visit. If needed, home visits (including Illness Visit) may be conducted by a clinical site nurse to perform the nasal swabs, except for V07, which should be done at the clinical site (as a physician should review the diary card).

§ Any unsolicited systemic adverse events occurring within the 30 minutes from study intervention administration will be recorded as immediate unsolicited systemic AE in the case report book.

\*\* The investigator or a designee will remind the parents / LAR to bring back the DC at the next visit and will answer any questions.

The parent / LAR will record information in the DC about solicited reactions from D01 to D22, and unsolicited AEs and AESIs from D01 to D29 after each study intervention administration.

†† The investigator or a designee will interview the parents / LAR to collect the information recorded in the DC and will attempt to clarify anything that is incomplete or unclear. In case of home visit(s) done by a clinical site nurse, the DC will be reviewed by a physician at the next clinical site visit.

†‡ Illness Visits: Additional nasal swab specimens for the detection of RSV and respiratory pathogens" (including COVID-19) will also be collected from pediatric participants in case of acute respiratory illness. All the nasal swab specimens will be collected in the recommended viral transport media tube and will be stored between -60°C and -80°C until ready to ship.

**Table 1.3: Schedule of activities for ad-hoc close contact participants**

Phase II Study, at least 1 Unplanned Illness Visit, at least 1 Unplanned Nasal Swab, Duration is limited to the Illness Visit(s)

Visit (V) / Contact*	Collection of information in the CRF	Illness Visit(s)
Study timelines - Days(D)		Not applicable
Visit Interval		ARI** symptoms during the 28 days following any administration of the study intervention to the close contact pediatric participant
Time windows (days)		Not applicable
Informed consent†	X	X
Collection of demographic data†	X	X
Allocation of participant number†	X	X
Nasal swab (NS)‡	X	UN0001 to UN000X§
Collection of End of Study status	X	At the end of the study intervention phase for the pediatric participant in close contact to ad-hoc participant

Abbreviations: CRF, case report form; ARI, acute respiratory illness

\* Additional unscheduled visits may be performed for safety reasons; information will be reported in the source documents.

[figure not shown]
† To be collected during the first illness visit.

‡ Illness Visits: All the nasal swab specimens will be collected in the recommended viral transport media tube and will be stored between -60°C and -80°C until ready to ship.

§ Ad-hoc close contact participants will provide a nasal swab sample for detection of vaccine virus transmission. The same nasal swab specimen may also be tested for respiratory pathogens (including COVID-19).

\*\* Acute respiratory illness includes upper and lower respiratory illness

**Figure 1.1: Graphical study design**

Detailed design is provided in Sections 4.1 and 1.1 of the protocol.

## 2 Objectives and Endpoints

**Table 2.1: Objectives and endpoints**

Objectives	Endpoints
Primary	

 
To describe the vaccine virus transmission in pediatric participants receiving placebo after the first study intervention administration
 
To describe the vaccine virus shedding in all pediatric participants with detected vaccine virus after each administration
 
To describe the vaccine virus stability in pediatric participants receiving placebo and ad-hoc close contact participants
 
	
 
Presence of vaccine virus in day (D)01, D04, D08, D11, D15, D18, and D22 nasal swabs, detected by quantitative reverse transcription polymerase chain reaction (RSVt qRT-PCR) Assay in pediatric participants receiving placebo
 
Titer of vaccine virus shedding in D01, D04, D08, D11, D15, D18, D22, D64, and D71 nasal swabs, quantified by RSVt qRT-PCR Assay in all pediatric participants
 
Difference in genetic sequence of mutated vaccine virus segments compared to the reference strain vaccine virus isolates in the vaccine virus positive swabs from pediatric participants receiving placebo and ad-hoc close contact participants
 

Secondary	
Immunogenicity	Immunogenicity

 
To evaluate the RSV A serum neutralizing and RSV serum anti-F immunoglobulin G (IgG) antibody responses to the study intervention after each study intervention administration in all pediatric participants
 
	
 
RSV A serum neutralizing antibody titers up to 28 days after the second administration (D01, D57, and D85)
 
RSV serum anti-F IgG Enzyme-linked Immuno-adsorbant Assay (ELISA) antibody titers up to 28 days after the second administration (D01, D57, and D85)
 

Safety	Safety

 
To assess the safety profile of the RSVt vaccine after each and any study intervention administration in pediatric participants.
 
	
 
Presence of any unsolicited systemic AEs reported in the 30 minutes after each study intervention administration
 
Presence of any solicited (ie, pre-listed in the participant's diary card [DC] and in the case
 

## 3 Statistical Considerations

### 3.1 Statistical Hypotheses

All analyses will be descriptive, no hypothesis will be tested.

### 3.2 Sample Size Determination

No sample size calculation was done as there are no statistical hypotheses in this study. A total of 100 pediatric participants (ie, 50 per study intervention group) are planned to be enrolled, based on clinical feasibility.

### 3.3 Populations for Analyses

For the purposes of analysis, the following analysis sets are defined:

Participant Analysis Set	Description
Randomized	Pediatric participants for whom a study intervention group has been allocated.
Safety Analysis Set (SafAS)	Pediatric participants who have received at least one study intervention administration. All pediatric participants will have their safety analyzed after each vaccination according to the study intervention they actually received, and after any vaccination according to the study intervention received at the first study intervention administration.  Safety data recorded for a vaccine received out of the protocol design will be excluded from the analysis (and listed separately).
Full Analysis Set (FAS)	Subset of randomized pediatric participants who received at least one study intervention administration.  Pediatric participants will be analyzed according to the study intervention to which they were randomized.

Per-protocol analysis set (PPAS)	
The PPAS is a subset of the FAS.
 
The pediatric participants presenting with at least one of the following relevant protocol deviations will be excluded from the PPAS:
 

• Pediatric participant did not meet all protocol-specified inclusion criteria or met at least one of the protocol-specified exclusion criteria

• Pediatric participant did not receive first study intervention administration at D01

• Pediatric participant received a study intervention at D01 other than the one that he / she was randomized to receive

• Preparation and / or administration of study intervention at D01 not done as per-protocol

• Pediatric participant NOT having at least 4 nasal swabs (with a valid result) between D08 and D22, with a maximum of 5 days' time interval between 2 consecutive nasal swabs

• Pediatric participant received a protocol-prohibited therapy before collection of nasal swab between D08 and D22

• Pediatric participant with an emergency unblinding performed by the investigator before collection of nasal swab at D22

• Pediatric participant who was RSV- exposed before study intervention administration at D01

Other analysis set	An analysis set will be used to document transmission of vaccine virus in the ad-hoc close contact participants

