The following medications will be prohibited during the study period for pediatric participants: intranasal and intraocular medications, and salicylate or salicylate-containing products.

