9.2 Analysis Sets

For the purposes of analysis, the following analysis sets are defined:

Participant Analysis Set	Description
Randomized	Pediatric participants for whom a study intervention group has been allocated.
Safety Analysis Set (SafAS)	Pediatric participants who have received at least one study intervention administration. All pediatric participants will have their safety analyzed after each study intervention administration according to the study intervention they actually received, and after any study intervention administration according to the study intervention received at the first study intervention administration. Safety data recorded for a vaccine received out of the protocol design will be excluded from the analysis (and listed separately).
Full Analysis Set (FAS)	Subset of randomized pediatric participants who received at least one study intervention administration Pediatric participants will be analyzed according to the study intervention to which they were randomized.
Per-protocol analysis set (PPAS)	The PPAS is a subset of the FAS. The pediatric participants presenting with at least one of the following relevant protocol deviations will be excluded from the PPAS: 
• Pediatric participant did not meet all protocol-specified inclusion criteria or met at least one of the protocol-specified exclusion criteria• Pediatric participant did not receive first study intervention administration at D01• Pediatric participant received a study intervention at D01 other than the one that he / she was randomized to receive• Preparation and / or administration of study intervention at D01 not done as per-protocol• Pediatric participant NOT having at least 4 nasal swabs (with a valid result) between D08 and D22, with a maximum of 5 days' time interval

	
between 2 consecutive nasal swabs
 
• Pediatric participant received a protocol-prohibited therapy before collection of nasal swabs between D08 and D22• Pediatric participant with an emergency unblinding performed by the investigator before collection of nasal swab at D22• Pediatric participant who was RSV exposed before study intervention administration at D01
Other analysis set	An analysis set will be used to document transmission of vaccine virus in the ad-hoc close contact participants

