Immediate events are recorded to capture medically relevant unsolicited systemic AEs which occur within the first 30 minutes after vaccination.

Reactogenicity / Solicited Reactions:

The **reactogenicity** of a vaccine refers to the property of such vaccine to be able to produce common "expected" adverse reactions (either systemic or at the injection site) and its associated signs and symptoms.

A solicited reaction is an "expected" adverse reaction (sign or symptom) observed and reported under the conditions (nature and onset) pre-listed in the protocol and CRF (eg, nasal congestion occurring between the day of vaccination and the next 21 days).

By definition, solicited reactions are considered as being related to the corresponding IMP administered.

For injectable vaccines, solicited reactions can either be solicited injection/administration site reactions or solicited systemic reactions

Administration Site Reactions:

An injection/administration site reaction is an AR at and around the injection/administration site of the IMP. Injection/administration site reactions are commonly inflammatory reactions.

Solicited injection / administration site reactions are reactions at and around the injection / administration site of the IMP observed and reported under the conditions (nature and onset) pre-listed in the protocol and CRF. It is considered by default as being related to the IMP administered at that site.

Note: « Administration site reaction » term is only to be used for vaccines that are not intended to be administered by injection.

Systemic AR:

Systemic ARs are all ARs that are not injection or administration site reactions. They therefore include systemic manifestations such as headache, fever, as well as localized or topical manifestations that are not associated with the injection or administration site (eg, erythema that is localized but that is not occurring at the injection site).

Solicited systemic reactions are systemic AEs observed and reported under the conditions (nature and onset) pre-listed in the protocol and CRF. Solicited systemic reactions occurring

during the specified collection period are always considered related to the IMP even if there is evidence of alternative etiology.

Unsolicited AE/AR:

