### 3.4.2 Primary Endpoints

#### 3.4.2.1 Vaccine virus transmission

Presence of vaccine virus detected by RSVt qRT-PCR ( $\geq$ LOD) in nasal swabs after the first vaccination (D01, D04, D08, D11, D15, D18, and D22) will be summarized in pediatric participants receiving placebo with 95% CIs:

- Number and percentage of participants with vaccine virus detected at each timepoint
- Number and percentage of participants with vaccine virus detected in at least one nasal swab

Transmissibility analyses will be performed on the SafAS and PPAS. Vaccine virus transmission is defined in [Section 4.2.1](#).

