### 3.4.3.3 Vaccine virus transmission

Presence of vaccine virus detected by RSVt qRT-PCR in nasal swabs after the second vaccination (D64 and D71) will be summarized in pediatric participants receiving placebo with 95% CIs:

- Number and percentage of participants with vaccine virus detected at each timepoint
- Number and percentage of participants with vaccine virus detected in at least one nasal swab

Transmissibility analyses will be performed on the SafAS. Vaccine virus transmission is defined in [Section 4.2.1](#).

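### As most naturally read, the PPAS prohibited-therapy criterion removes a placebo child whose positive swab came before the therapy, so a valid transmission event drops out of the per-protocol rate

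*SAP*

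**What the plan says.** SAP 3.3 defines the PPAS by exclusions at the level of the child: "The pediatric participants presenting with at least one of the following relevant protocol deviations will be excluded from the PPAS". One of these deviations is "Pediatric participant received a protocol-prohibited therapy before collection of nasal swab between D08 and D22". Protocol 9.2 has the same criterion with the last noun in the plural: "Pediatric participant received a protocol-prohibited therapy before collection of nasal swabs between D08 and D22". Protocol 6.8 says what is prohibited: "The following medications will be prohibited during the study period for pediatric participants: intranasal and intraocular medications, and salicylate or salicylate-containing products".

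For the primary transmission endpoint, SAP 3.4.2.1 reports placebo children at each timepoint and also "Number and percentage of participants with vaccine virus detected in at least one nasal swab", covering D01 to D22. On the analysis sets it says: "Transmissibility analyses will be performed on the SafAS and PPAS". Neither set is named as the main one. For transmission after the second dose, SAP 3.4.3.3 names one set only: "Transmissibility analyses will be performed on the SafAS".

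Neither document makes an exception for a child who was positive before the therapy, limits the criterion to later swabs, or plans a sensitivity analysis on this point.

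**The concern.** A child's status on the summary of at least one positive swab is fixed by the first positive. A nasal or ocular product given afterwards could at most hide virus in later swabs. It cannot undo a detection that came before it. Excluding the child for that therapy therefore guards against no error in this endpoint and removes a true event.

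The trigger also occurs after randomization, and infection may cause it. Protocol 10.2.1 uses nasal congestion as its example of a solicited reaction: "nasal congestion occurring between the day of vaccination and the next 21 days". A placebo child who acquires the vaccine virus could become congested and be given a nasal product. If that happens more often in infected than in uninfected children, the PPAS selects against events.

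The PPAS carries some weight in interpretation. It also excludes children exposed to RSV before dosing, and Protocol 4.2 expects infants with earlier RSV infection to shed less and so to transmit less. In the unredacted text it is the only transmission set with that restriction, so a zero there could be taken as no transmission to RSV-naive children.

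**Working it through.** **Plan's own figure.** SAP 3.2 plans 100 children, which at 1:1 gives 50 on placebo. The number rests on feasibility. There is no power or precision calculation to reproduce.

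**Inputs from the documents.** Proportions get two-sided 95% Clopper-Pearson intervals (SAP 3.4.1). Exclusion is per child and the endpoint is at least one positive swab (SAP 3.3 and 3.4.2.1).

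**Inputs assumed.** The documents give no transmission rate and no treatment rate. Let π be the true transmission rate in placebo children, and t1 and t0 the shares of infected and uninfected children whom the criterion excludes.

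**Step 1: does the criterion reach a child who is already positive?** Take a placebo child positive at D08 and treated at D10. The D11 to D22 swabs follow the therapy.

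- If therapy before any swab in the D08-D22 window triggers exclusion, which is the natural reading, the child is out and the D08 event goes too.
- If therapy must precede the window's swabs as a whole, this child stays. A child positive at D04 and treated before D08 is still excluded, although D04 counts for the primary endpoint.

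A detected event can be lost under either reading, more often under the first. Therapy first taken after the last swab of the window excludes nobody.

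**Step 2: expected PPAS rate.**

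Expected rate = π(1 − t1) / [π(1 − t1) + (1 − π)(1 − t0)]

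With π = 0.10 and t0 = 0.10, the uninfected term is 0.90 × 0.90 = 0.81.

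| t1 | Calculation | Expected PPAS rate |
|---|---|---|
| 10% | 0.09 / (0.09 + 0.81) | 10.0% |
| 20% | 0.08 / (0.08 + 0.81) | 9.0% |
| 30% | 0.07 / (0.07 + 0.81) | 8.0% |
| 50% | 0.05 / (0.05 + 0.81) | 5.8% |

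With π = 0.05 and the same t0, the four values are 5.0%, 4.5%, 3.9% and 2.8%. When t1 = t0 the criterion adds no bias on average. When t1 exceeds t0 the rate is too low.

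**Step 3: small counts, extreme case.** The only infected child is treated and excluded, and no uninfected child is.

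- Assumed PPAS of 40 placebo children: 1/40 = 2.5% (0.1 to 13.2) becomes 0/39 = 0% (0 to 9.0).
- All 50 planned placebo children: 1/50 = 2.0% (0.1 to 10.6) becomes 0/49 = 0% (0 to 7.3).

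**Step 4: does it suffice to restore only the positives?** Keeping treated positives while dropping treated negatives sets t1 = 0 with t0 above zero, which biases the rate upward. At π = 0.10, t0 = 10% gives 0.10 / (0.10 + 0.81) = 11.0%, and t0 = 30% gives 0.10 / (0.10 + 0.63) = 13.7%. The remedy therefore has to treat positive and negative children alike.

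**The case against.** The strongest reply is that the SafAS already deals with this. It keeps every dosed child whatever therapy was taken, it is reported for the same endpoint, and a gap between the two rates would show the loss. This stands, and it limits the point. A reader might infer that transmissions disappear from the trial's results. They do not; they are missing from the PPAS rate only, and the post-dose-2 analysis in SAP 3.4.3.3 is on the SafAS. What remains is that the PPAS is one of the two stated sets and nothing planned would explain a gap.

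A second reply is that the direction of bias is not established. This also stands. The congestion example is part of a general definition of reactions after vaccination and does not describe placebo children infected by contact. The trial was planned to start in Q4, in daycare and sibling groups, so uninfected children may be congested and treated as well. The products are prohibited, so use may be rare.

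A third reply is that the wording is open: singular in the SAP, plural in the protocol, with no statement whether any or all of the window's swabs are meant. That is correct, and it is itself a reason to rewrite the criterion.

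**Conclusion.** The point holds for the PPAS. On the natural reading of SAP 3.3 and Protocol 9.2, therapy given after a positive swab removes the child and a valid transmission event with it. The downward bias is conditional on infected placebo children being treated more often than uninfected ones. Its size is unknown because the documents give neither rate. Under the assumptions shown it runs from none (10.0% stays 10.0%) to a fall to 5.8%, and with a single event the estimate can reach zero.

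A reader might go further and infer that one or two lost events would change the trial's conclusion. The documents do not support that. All analyses are descriptive, no threshold or decision is tied to the PPAS, and the illustrative intervals overlap widely. The defect is a correctable weakness in one of the two primary transmission sets.

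**What to change.** Amend SAP 3.3 and Protocol 9.2 in the same words:

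- Apply the prohibited-therapy criterion to swabs and not to children, and state which swabs it covers, including how therapy before D08 counts.
- Count a positive swab collected before the therapy as a transmission, and keep that child in the PPAS with respect to this criterion.
- Keep treated children without an earlier positive as well, using their swabs up to the therapy, so that membership does not depend on the result.
- State that swabs set aside in this way do not count against the separate requirement of at least four valid swabs between D08 and D22. Otherwise a child treated at D10 keeps only the D08 swab of that window and is excluded by the other route.
- Add a sensitivity analysis that keeps all treated children with all their swabs. A first positive after the therapy is then counted.
- List beside the PPAS rate every vaccine-virus-positive placebo child excluded from the PPAS, with the reason.

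The cost is wording in two documents and slightly more analysis work, with no new visits or samples. The drawback is that some treated negative children are kept with shorter swab follow-up, so a later infection could be missed in them. The sensitivity analysis and the SafAS rate show how much that matters.
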